2.5 Observations and Measurements

2.5.1 Lavage Processing

Tracheal lavage fluid will be placed on ice and transported immediately to our laboratory. A sample of 0.25cc or less will be removed for cell count and differential count. We will do total cell counts using tryptan blue to check viability of cells. Remaining whole fluid will be centrifuged at 1500 rpm for 15 minutes at 4° C and supernatants frozen in aliquots.

2.5.2 Neutrophil assessment and purification

Neutrophils will be counted in the tracheal lavage and peripheral blood with a HEMAVET analyzer (Drew Scientific). Neutrophils will be purified by immunomagnetic bead-mediated negative selection with biotin-labeled antibodies (e-biosciences) specific for CD11b, CD62L, CD54, CD32, CD88, and CD66b. Flow cytometry will be used for assessment of neutrophil surface receptor presence.

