	
5. Provide informed consent.
 
Exclusion:
 
 1. Active pulmonary disease within 5 days prior to enrollment 2. On immunosuppressive medications 3. Previous tracheal surgery 4. On azithromycin 5. Diabetes 6. Pregnancy 7. Smoking history of less than 6 weeks prior to surgery 8. Surgery or intubation within 5 days of surgery 9. Planned surgical procedure involving neck or thoracic regions 10. Active pulmonary disease 11. Autoimmune disease (HIV, AIDS, Rheumatoid Arthritis) 12. Hepatitis B or C, or active Hepatitis A 13. Cancer 
Healthy Controls: Inclusion:
 
 1. Ages 18 to 65 2. Provide informed consent.
Measurements	
Lavage Processing
 
Tracheal lavage fluid specimens will be placed on ice and transported immediately to our laboratory. A sample of 0.25cc or less will be removed for cell count and differential count. We will do total cell counts using tryptan blue to check viability of cells. Remaining whole fluid will be centrifuged at 1500 rpm for 15 minutes at 4° C and supernatants frozen in aliquots.
 
Neutrophil assessment and purification
 
Neutrophils will be counted in the tracheal lavage and peripheral blood with a HEMAVET analyzer (Drew Scientific). Neutrophils will be purified by immunomagnetic bead-mediated negative selection with biotin-labeled antibodies (e-biosciences) specific for CD11b, CD11c, CD14, CD16 CD62L, CD54, CD32, CD88, and CD66b. Flow cytometry will be used for assessment of neutrophil surface receptor presence.
 
Reactive Oxygen Species (ROS) determination
 
Neutrophil production of ROS will be assessed with the fluoro-probe dihydrorhodamine.
 
Interleukin Assays
 
Accumulation of interleukin 1 (IL-1), IL-4, IL-6, IL-8, IL-10, IL-12, IL-17, IL-23p19, (transformin growth factor 1 (TGF β-1) and tumor necrosis factor alpha (TNF-α) in culture will follow stimulation with formylated peptides by immunosorbent assay (ELISA) for human

CONFIDENTIAL: This document is the intellectual property of [name]. Acceptance of this document constitutes the agreement by the recipient that no unpublished information contained herein will be published or disclosed without prior written approval.

DoCTR

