	
cytokines (R&D Systems, Minneapolis, MN).
 
Toll-like Receptors (TLR) Determination of TLR-2, TLR-4 and TLR-9 and Mitochondrial DNA will be done by PCR.
 
Neutrophil extracellular traps (NETs) formation Neutrophil cells will be stained and photographic documentation of the NET presence will be documented.

Statistical Methodology
	
The primary aim of this study is to describe the inflammatory changes that result in a neutrophil surface receptor expression unique to the interaction between the trachea and ETT resulting in sore throat. Blood samples will be obtained and neutrophil cells (PMN) will be isolated for analysis at the same time intervals as the tracheal lavage samples. Individual indicators of inflammation (PMN, cytokines, clusters of differentiation –CD, TLR's as described above) will be compared to baseline values of these variables measured at time zero. We will compare neutrophil (PMN) changes between patients who developed sore throat and those who do not by using the Wilcoxon rank sum test, since we expect the data to be non-normally distributed. With a sample size of 60 patients, we will have at least 80% power to detect large differences (Cohen's $D \geq 0.8$) between the sore throat and non-sore throat groups with an alpha level of 0.05 and assuming that half of the participants report a sore throat following intubation. As our pilot study is exploratory, we did not inflate our sample size to account for multiple testing. We will confirm any identified associations found in our pilot study with a future larger study. Subjects who undergo intubation attempts $\times 2$ or greater will be considered a subset population and not part of the 60 evaluable patients. Assuming that lack of sore throat relates to anti-inflammation, measuring a biomarker such as IL-10, may provide information on the regulatory function of this cytokine. We have observed that IL-10 at a concentration of 200 pg/ml generated by PMNs inhibited reactive oxygen species burst from alveolar macrophages challenged by LPS. Power analysis was conducted for two tailed T-test using the following assumptions: a standard deviation of 100 pg/ml. A difference of 75 pg/ml between the two groups will be considered a significant difference. We will need approximately 30 patients per group for an alpha 0.05 and Beta of 0.2.

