response to inflammatory cytokines. Clusters of differentiation are used for identification of neutrophils, to determine migration, phagocytosis and activation. Some of the CDs expressed in the neutrophil surface include those related to neutrophil adhesion¹⁹ (CD11b, CD11c, CD16 CD62L, and CD54); Immunoglobulins (CD32) and anaphylatoxins (CD88, CD66b)²⁰. The effects of granulocyte-macrophage colony stimulating factor (GM-CSF), are well described regarding encoding of CDs in response to bacteria and DAMPs²¹; with significant enhancement of the pro-inflammatory activity of PMNs, and is consistent with the concept of a significant biosynthetic capacity for PMN cells.

Neutrophils produce large quantities of reactive oxygen species. Although reactive oxygen species (ROS) are generated by neutrophils to control infection, this activity may also alter local healthy tissue. Hydrogen peroxide and superoxide are generated during phagocytosis of particles or elevated concentration of chemoattractants²². A sign of neutrophil activation is an acute increase in oxygen consumption (respiratory burst) that is mediated by a membrane-bound complex, nicotinamide adenine dinucleotide phosphate (NADPH)-dependent oxidase²³. NADPH mediates formation of superoxide anion after dismutation to hydrogen peroxide, which in turn is involved in promoting formation of secondary reactive products, such as singlet oxygen, hypochlorous acid and hydroxyl radicals. The end point of this process is neutrophil degranulation with subsequent enzyme degradation of host and microbial tissues.

Regulatory PMN cells are important for host protection against injury. PMN cells have demonstrated dual properties in regulating a specific response to sterile and non-sterile injury by using different mechanisms to induce inflammation or anti-inflammation (immunosuppression)²⁴. During infectious injury mediated by gram positive, gram negative bacteria, fungus, PMN may influence activation of T cells which produce interferon γ (IFN- γ), and in turn IFN- γ acts as a potent activator of PMN locally²⁵; or can involve Toll -like Receptors (TLRs) such as TLR-2, TLR-4 and TLR-9²⁶. We are interested in studying the response of PMNs to injury secondary to the ETT, by analyzing several indicators of PMN activation regarding inflammation and anti-inflammation.

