2.5.7 Primary Outcome Measures

The study is aimed at identifying neutrophil surface changes that occur during tracheal injury secondary to endotracheal intubation and to correlate them with the development of sore throat.

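### As written, neutrophils are purified by negative selection against markers that the protocol itself places on the neutrophil surface, and no separate depletion set or single flow-cytometry panel is stated

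*Combined protocol and SAP*

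**What the plan says.** Section 2.5.2 describes the isolation step: "Neutrophils will be purified by immunomagnetic bead-mediated negative selection with biotin-labeled antibodies (e-biosciences) specific for CD11b, CD62L, CD54, CD32, CD88, and CD66b". The same sentence in the synopsis (Measurements) uses a longer list: "specific for CD11b, CD11c, CD14, CD16 CD62L, CD54, CD32, CD88, and CD66b".

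In both places the next sentence turns to measurement and names no marker: "Flow cytometry will be used for assessment of neutrophil surface receptor presence".

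Section 2.1 explains what these markers are. "Some of the CDs expressed in the neutrophil surface include those related to neutrophil adhesion", it says, and then gives the list: "CD11b, CD11c, CD16 CD62L, and CD54); Immunoglobulins (CD32) and anaphylatoxins (CD88, CD66b". It also states what they are for: "Clusters of differentiation are used for identification of neutrophils, to determine migration, phagocytosis and activation".

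Section 2.5.7 sets the primary outcome as "identifying neutrophil surface changes that occur during tracheal injury secondary to endotracheal intubation", to be correlated with sore throat. The synopsis (Statistical Methodology) and section 2.5.9 name the variables to be compared with baseline, beginning "Individual indicators of inflammation (PMN, cytokines, clusters of differentiation", and refer back to the earlier description for their content.

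**The concern.** In negative selection, antibodies label the unwanted cells, the beads pull those cells out, and the unlabelled cells are kept. The documents do not define the term otherwise. A step of this kind that is meant to yield neutrophils should therefore use antibodies to other cell types. The text instead names antibodies to markers that section 2.1 places on neutrophils.

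This matters because the cells the step yields are the natural source of the surface-receptor data behind the primary outcome. The protocol also expects these markers to vary with condition: section 2.1 cites a study of diabetic microangiopathy in which CD11b was raised and CD62L lowered. Selecting cells on such markers would tie which cells are kept to the quantity being measured.

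If the sentence is only a drafting slip, reproducibility is still at stake. Section 2.5.10 says that associations found here will be confirmed in a larger study. That needs the same isolation method and the same panel, and neither can be read from the text.

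**Working it through.** The plan gives no figure for this point, so there is none to reproduce. The check compares three lists.

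| Marker | Neutrophil surface list, section 2.1 | Selection list, synopsis | Selection list, section 2.5.2 |
|---|---|---|---|
| CD11b | yes | yes | yes |
| CD11c | yes | yes | no |
| CD14 | no | yes | no |
| CD16 | yes | yes | no |
| CD32 | yes | yes | yes |
| CD54 | yes | yes | yes |
| CD62L | yes | yes | yes |
| CD66b | yes | yes | yes |
| CD88 | yes | yes | yes |
| **Total** | **8** | **9** | **6** |

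1. **Overlap with the neutrophil list.** In section 2.5.2, 6 of 6 selection targets are on the section 2.1 list and 6 − 6 = 0 are off it. In the synopsis, 8 of 9 are on it and 9 − 8 = 1 is off it, namely CD14.

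2. **Literal reading.** Every antibody named in 2.5.2, and all but one in the synopsis, would bind cells that the step is meant to keep. The neutrophils would be removed or, if depletion were partial, kept according to their level of these receptors.

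3. **Drafting-merge reading.** The synopsis list is exactly the eight section 2.1 markers plus CD14 (8 + 1 = 9). Section 2.1 describes such markers as tools for identifying neutrophils and judging their activation. The statistical text treats them as measured indicators, and the flow-cytometry sentence that follows has no list of its own. The list therefore looks like the read-out panel, moved into the wrong sentence. This is an inference, but a well-supported one.

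4. **What is missing on that reading.** No depletion set is given. Off the neutrophil list, 2.5.2 names no antibody, and the synopsis names only CD14 without giving its role. The read-out panel would be nine markers in one place and six in the other. The difference is 9 − 6 = 3 markers: CD11c, CD14 and CD16. Six markers are common to all three lists.

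5. **Link to flow cytometry.** Neither 2.5.2 nor the synopsis says whether flow cytometry is run on the purified cells or on unpurified blood and lavage. Any effect of the selection step on the surface-marker results depends on that.

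**The case against.** The strongest reply is that this is a wording slip which no laboratory would carry out. Complete loss of the neutrophils would be noticed at once, and the surrounding text shows that the list was meant as the read-out. The study is also described as an exploratory pilot. Much of this stands: the merge is the likelier explanation, and the point is an internal contradiction in the text, not a flawed design. But the explanation does not supply the missing depletion antibodies or say which of two differing lists is the panel.

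A second reply is that part of the analysis does not rest on this step. Section 2.5.2 has neutrophils counted in lavage and blood with an automated analyzer, and section 2.5.1 sets aside a lavage aliquot for cell and differential counts. The rank-sum comparison in section 2.5.9 is of neutrophil changes, which may include counts. This stands, and it limits the point to the surface-marker part.

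A reader might infer that the comparison of patients with and without sore throat is biased. The documents do not support that. It would need literal execution, partial depletion and flow cytometry on the retained cells, and the last is not stated. A reader might also infer that nine versus six markers changes the error rate or the sample size. It does not: section 2.5.10 makes no allowance for multiple testing, so no stated alpha or sample size depends on the panel. Nine and six are panel sizes only if the list is really the read-out; as written, both are selection lists.

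Finally, full reagent detail need not sit in the protocol. That is fair, and a reference to a laboratory procedure would do.

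**Conclusion.** The point holds as an internal contradiction in a method that serves the primary outcome, and it should be fixed. All six selection targets in section 2.5.2, and eight of nine in the synopsis, are markers that section 2.1 assigns to the neutrophil surface. The two lists differ by three markers. These counts are certain.

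The conclusion rests on two assumptions: that negative selection has its ordinary meaning, and that the receptors in the primary outcome, which section 2.5.7 does not name, are the markers listed elsewhere in the protocol. Both are reasonable. No bias can be sized from the documents and none is claimed. What is established is that the isolation step is wrong as worded and that, if the list is the read-out, the panel is not settled.

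**What to change.** Amend section 2.5.2 and make the synopsis agree with it.

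- **Selection.** Replace the purification sentence with one saying that depletion uses antibodies to non-neutrophil cells, and that no marker read as a neutrophil outcome is used for depletion. Name the antibodies, or cite the laboratory procedure that does.
- **Read-out.** Give one flow-cytometry panel, identical in both places. Say whether CD11c and CD16 belong to it, and whether CD14 is a depletion marker or a read-out marker.
- **Cells analysed.** State whether flow cytometry is run on purified or unpurified cells.

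The cost is a few sentences and a check of the reagents in use. No extra patients or samples are needed.

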2.5.3 Reactive Oxygen Species (ROS) determination

Neutrophil production of ROS will be assessed with the fluoro probe dihydrorhodamine.

2.5.4 Interleukin Assays

Accumulation of interleukin 1 (IL-1), IL-4, IL-6, IL-8, IL-10, IL-17, IL-23p19, transformin growth factor 1 (TGF β -1) and tumor necrosis factor alpha (TNF- α) in culture will follow stimulation with formylated peptides by immunosorbent assay (ELISA) for human cytokines (R&D Systems, Minneapolis, MN).

2.5.5 Toll-like Receptors (TLR)

Determination of TLR-2, TLR-4, TLR-9 and mitochondrial DNA will be done by PCR.

2.5.6 Neutrophil extracellular traps (NETs) formation

Neutrophil cells will be stained and photographic documentation of the NET presence will be documented.

2.5.7 Primary Outcome Measures

The study is aimed at identifying neutrophil surface changes that occur during tracheal injury secondary to endotracheal intubation and to correlate them with the development of sore throat.

2.5.8 Exploratory Secondary Outcome Measures

To analyze the determine the presence and role of GMSTM1 in all the specimens collected and in the prospective human donors.

Evaluate the role of autophagy 1 [ATG16L1] genetic polymorphisms of neutrophils in patients with and without postoperative airway inflammation or ventilator-associated pneumonia. ¶

2.5.9 Statistical Methods

CONFIDENTIAL: This document is the intellectual property of [name]. Acceptance of this document constitutes the agreement by the recipient that no unpublished information contained herein will be published or disclosed without prior written approval.

DoCTR

The primary aim of this study is to describe the inflammatory changes that result in a neutrophil surface receptor expression unique to the interaction between the trachea and the ETT and result in sore throat. Blood samples will be obtained and neutrophil cells (PMN) will be isolated for analysis at the same time intervals as the tracheal lavage samples. Individual indicators of inflammation (PMN, cytokines, clusters of differentiation –CD, TLR's as described above) will be collected at specific pre-determined times and will be compared to baseline values of these variables measured at time zero. We will compare neutrophil (PMN) changes between patients who developed sore throat and those who do not by using the Wilcoxon rank sum test, since we expect the data to be non-normally distributed.

2.5.10 Sample Size

With a sample size of 60 evaluable patients, we will have at least 80% power to detect large differences (Cohen's $D \geq 0.8$) between the sore throat and non-sore throat groups with an alpha level of 0.05 and assuming that half of the participants report a sore throat following intubation. As our pilot study is exploratory, we did not inflate our sample size to account for multiple testing. We will confirm any identified associations found in our pilot study with a future larger study. All subjects that undergo intubation attempts times 2 or more, will not be considered evaluable for the primary aim of this research. However, these patients will be considered as a subset and of possible interest for analysis and outcome measures.

Data analysis of the blood neutrophil changes occurring under different laboratory conditions will be analyzed using a Student-t test to compare them with changes observed in the injured airway neutrophils. A total of 25 evaluable patients will provide sufficient blood neutrophils to determine differences.

3.0 Management of Intercurrent Events

3.1 Adverse Experiences

The investigator will closely monitor subjects for evidence of adverse events. All adverse events will be reported and followed until satisfactory resolution. The description of the adverse experience will include the time of onset, duration, intensity, etiology, relationship to the study procedures (none, unlikely, possible, probable, highly probable), and any follow up treatment if required.

3.2 Premature Discontinuation

If a subject withdraws from the study, the subject will be replaced in order to provide the required number of evaluable subjects. Subjects will be withdrawn if the investigator decides that discontinuation is in the best interest of the subject, or the subject requests withdrawal from the study.

3.3 Potential Risks

3.3.1 Potential risks from ETT saline lavage

By using sterile normal saline solution we minimized the impact of the irrigation on the trachea since the osmolality of the saline is similar to the osmolality of the serum. The collection of tracheal

CONFIDENTIAL: This document is the intellectual property of [name]. Acceptance of this document constitutes the agreement by the recipient that no unpublished information contained herein will be published or disclosed without prior written approval.

DoCTR

secretions will be performed by trained personnel. Wall suction will be set to a minimum in order to minimize tracheal injury and to comply with standards of medical care. Although the endotracheal tube does not contain any particular medication, its presence may induce sore throat (reason for the study). The ET tube is being placed as standard of care for patients undergoing general anesthesia. The intrinsic risks related to the placement of the endotracheal tube are beyond the scope of our research.

3.3.2 Potential risks from blood draw

Discomfort, bruising, and/or bleeding at the site of the needle injection. Every attempt will be made to collect the blood sample from an indwelling venous or arterial catheter. All samples will be collected using standard medical techniques by trained personnel.

3.3.3 Potential risk from loss of confidentiality

One risk of participating in this study is that confidential information may be accidentally disclosed. We will use our best efforts to keep the information secure, and the risk of accidental disclosure is very small. All samples and health information will be de-identified and assigned a study ID number. Statisticians involved in the project will have access only to de-identified data for the purposes of analysis. The original informed consents will be kept by the PI and a copy will be given to all subjects. Neutrophil surface activation data samples will be kept confidentially. Any information obtained from medical records will be coded, with a key to the code linking code numbers to names kept at a separate location, under lock and key. 1) The link to identifiers will be destroyed at the end of the study. We have no evidence to suggest that testing will provide evidence of previously undiagnosed or unrecognized illness, or susceptibility to illness. 2) We will not use samples for any purpose other than to perform tracheal and blood neutrophil analysis. 3) Data will be stored under lock and key (office, file cabinet) and only the investigators will have access. If data are published, there will be no link to identifiers. Study data will not be revealed to any organization or individuals.

3.4 Procedures to Minimize Potential Risks

[figure not shown]
Study related procedures will be conducted in the operating room under the general supervision of the PI, a board-certified anesthesiologist, thoroughly trained and experienced in intubation, tracheal lavage, and blood collection. Subjects will be monitored through-out the study period by trained personnel. Subjects will be informed that participation is voluntary and they may refuse to participate and may withdraw from the study at any time without penalty. Subjects will be told that in the event of a physical injury as the direct result of study procedures, they will be cared for by a member of the investigating team at no cost, within the limits of the Washington University compensation plan.

3.5 Data and Safety Monitoring Plan

The principal investigator will monitor the study for any adverse events and serious adverse events per the institutional guidelines. All unanticipated problems will be reported to the HRPO. Should there be a serious adverse event that occurs that increases the risks to the participants, the study will be stopped, an investigation will be conducted, and a findings report will be generated before the study is resumed. The specific monitoring plan for this investigation is commensurate with the risks

CONFIDENTIAL: This document is the intellectual property of [name]. Acceptance of this document constitutes the agreement by the recipient that no unpublished information contained herein will be published or disclosed without prior written approval.

DoCTR

and the size and complexity of the investigations planned. These risks, as described above, are small. Based on these considerations, we will utilize a monitoring plan that involves:

- (1) Engaging a colleague not involved in the study to serve in a monitoring capacity. Based on the small size and low-risk, we envision only a third person (the colleague), not a full DSMB.
- (2) A specific plan for submitting Adverse Event Reports to the IRB. That plan is detailed in the department's SOP for Adverse Event Reporting (attached).

